1.6. Objectives of the NOTABLE Trial

Is a vNOTES adnexectomy at least as effective compared to the standard transabdominal laparoscopic approach (LSC) for removing a benign adnexal mass without spill?

Secondary research questions are:

- Do more women treated by vNOTES prefer to leave the hospital on the day of surgery compared to LSC?
- Do women treated by vNOTES suffer from less pain compared to women treated by LSC in the first postoperative week?
- Is the removal of a benign adnexal mass by vNOTES faster compared to LSC?
- Does a vNOTES cause more pelvic infection or other complications compared to LSC?
- Does a vNOTES result in more hospital readmissions during the first six weeks following surgery compared to LSC?
- Does a vNOTES approach result in more women reporting dyspareunia, less quality of life or less sexual wellbeing at 3 or 6 months after surgery when compared to women treated by LSC?
- What are the costs of a vNOTES compared to LSC?

2. TRIAL DESIGN

2.1. Design

A single centre, single-blinded, parallel group randomised, non-inferiority efficacy trial.

2.2. Simple pilot randomised trial: minimal extra workload

This is a pilot randomised trial aiming to demonstrate that vNOTES is at least as effective compared to the classical gold standard approach of laparoscopy for successfully removing benign adnexal masses without spill (non-inferiority design). In this phase of HTA the trial will need the participation of only one centre. To make this practicable, trial procedures are kept simple, with the minimal extra workload placed on participating clinicians, beyond that required to treat their patients. This will be achieved by simple entry procedures, the use of standard local diagnostic and surgical regimens, routine follow-up of patients (with few additional hospital visits or tests to be performed above those done as part of standard care), minimising documentation and largely patient-based evaluation of outcome (PROM).

2.3. Time schedule

Based upon the mean number of laparoscopic adnexectomies performed annually at the department of Obstetrics and Gynaecology of the participating centre (36) we estimate that the duration of recruitment will be 21 months. Based upon the follow up (6 months) and the period of analysis/reporting (3 months) the total study period will be 2.5 years.

3. ELIGIBILITY, CONSENT AND RANDOMISATION

3.1. Screening and consent prior to surgery

All women regardless of age and parity presenting with a symptomatic or asymptomatic persistent benign adnexal mass on clinical examination confirmed by ultrasound are eligible for inclusion. The diagnosis of benign adnexal mass will be based upon the prospectively IOTA validated simple ultrasound rules to distinguish between benign and malignant adnexal masses (10). All the ultrasound examinations will be reviewed before the randomisation by a named operator with competence in gynaecological ultrasound and experience in applying the simple rules. The need for additional examinations (CAT scan or CA-125) is based upon good clinical practice.

The trial will be introduced to the eligible women in the outpatient clinic and a comprehensive, evidence-based patient information sheet will be provided at the clinic visit. Participant information sheets and consent form will be provided in Dutch.

Before the procedure, the women will be given a chance to discuss the risks and benefits of vNOTES or laparoscopy for removing the adnexal mass, the process of randomisation and the follow-up requirements with the consultant gynaecologist. It will be carefully explained that the final decision about eligibility will be taken during the surgical procedure and is dependent on the findings; therefore consent will be required before the procedure, in every instance.

Over the past 4 years 145 laparoscopic adnexectomies were performed at the department of Obstetrics and Gynaecology of the participating centre. The mean number of procedures per year (SD) is 36 (\pm 13). About 69 % of the eligible women should be willing to participate in the proposed study to include the required amount of participants within 2.5 years (see: Section 6.1. Sample size on pages 31-32).

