3.2. Determining eligibility

All women regardless of age and parity presenting with a symptomatic or asymptomatic persistent benign adnexal mass on clinical examination who provide consent to participation are eligible in the NOTABLE trial based on the findings of the ultrasound findings and will be randomised before the procedure.

The following inclusion/exclusion criteria will be applied to assess eligibility:

Inclusion criteria:

- All women regardless of age and parity with a symptomatic adnexal mass presumed to be benign based on ultrasound examination by applying the IOTA simple rules
- All women regardless of age and parity with an asymptomatic persistent adnexal mass presumed to be benign based on ultrasound examination by applying the IOTA simple rules

- Written informed consent obtained prior to surgery

Exclusion criteria:

- History of hysterectomy by any technique
- History of rectal surgery
- Suspected rectovaginal endometriosis
- Suspected endometriotic cyst
- Solid adnexal mass
- High suspicion of adnexal malignancy based on clinical, ultrasound or biochemical findings
- History of pelvic inflammatory disease, especially prior tubo-ovarian or pouch of Douglas abscess
- Active lower genital tract infection e.g. Chlamydia, N. gonorrhoeae
- Virginity
- Pregnancy
- Need for other uterine surgical intervention (i.e. endometrial ablation, resection, myomectomy or hysterectomy)
- Additional pathology necessitating hysterectomy
- Failure to provide written informed consent prior to surgery

Obesity (Body Mass Index or BMI > 30), nulliparity or large diameter of the cyst are not considered to be an exclusion criterion per se. We will only stratify for the diameter of the cyst because this parameter was perceived by the gynaecological surgeon as the most important one to influence the difficulty of the procedure. Stratification for three parameters in a small pilot randomised trial with a limited number of participants is not sensible.

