3.3. Randomisation

If the woman is eligible for the NOTABLE trial, the trial secretary will obtain a randomised allocation the day before surgery. This will be done using a randomisation list generated by a free computer software program offered by Research Randomizer (<https://www.randomizer.org>). The random sequence generation will be concealed using sequentially numbered opaque sealed envelopes. The envelope will be opened by the nurse assistant on the day of surgery for practical logistic reasons. We will use stratified randomisation according to the cyst diameter. See 3.5 Stratification of randomisation.

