3.5. Stratification of randomisation

A blocked randomisation procedure will be used to avoid chance imbalances for the parameter 'cyst diameter'. We preferred not to use minimisation because this trial was not funded and we therefore could not afford to buy licenses for a computer-based algorithm for minimisation. Although parity and BMI may be prognostic parameters influencing the chances of the successful removal of the adnexal mass, we preferred to limit the stratification to one parameter for reasons of simplicity based on what is affordable to conduct the present research. It was not considered appropriate to use three strata in a small pilot study including a small number of participants.

To avoid any possibility of foreknowledge, the randomised allocation will not be given until all eligibility and stratification data have been given.

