4. TREATMENT ALLOCATIONS

4.1. Surgical procedures

The principal investigator, who has training and experience in both laparoscopy and NOTES, will perform all surgical procedures. He is therefore not blinded. All vNOTES participants will be blinded by three superficial “mock” skin incisions similar to those routinely done with the laparoscopic technique. The wound bandages will be left in place until the day 7 postoperative control to be removed by the coordinating investigator who will state at that moment that the wound healing has left an almost invisible scar as expected. This procedure aims to blind the participants, personnel and outcome assessors. The practice of performing “mock” incisions should not be considered as unethical: it is a procedure that has already been used in some surgical trials to minimise performance and detection bias whenever a subjective outcome is measured (22). The decision to use “mock” surgery is based on the clinical equipoise regarding the balance between benefits and adverse events for the two interventions under comparison (23).

4.1.1 vNOTES adnexectomy

This is the surgical procedure done in the intervention arm of the NOTABLE trial.

Clindamycin vaginal cream is administered on admission of the study participant to the outpatient ward.

The patient is placed in lithotomy position in a vacuum mattress. The abdomen, the vulva and the vagina are disinfected with an alcoholic betadine solution and draped. A Foley catheter is inserted into the bladder.

Three superficial skin incisions are made, one deep in the umbilicus and one in the left and right iliac fossa lateral of the epigastric vessels, and in the suprapubic region. The small vertical intraumbilical skin incision is closed with a monocryl 3/0 intradermal suture. Wound bandages are applied to all three skin incisions.

A 2.5 cm posterior colpotomy is made using a cold knife. The pouch of Douglas is opened using cold scissors. A Gelpoint Mini (Applied Medical) is used as vNOTES port and is inserted into the pouch of Douglas. CO₂ is insufflated until a maximal intraperitoneal pressure of 15mmHg. An optic is inserted and the peritoneal cavity is inspected. The patient is now placed in Trendelenburg position. The small intestine is lifted out of the pelvis.

The ureter is identified, but not routinely dissected. It is only dissected if it cannot be identified transperitoneally. The proximal end of the Fallopian tube is coagulated at its origin into the uterus

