4.1.3 Failure of procedure

Occasionally, surgical removal of a benign adnexal mass by any of the two techniques may not be completed according to the random sequence generation because of technical limitations or unexpected findings such as extensive adhesions or unexpected malignancy. Successful vNOTES or laparoscopic removal of a benign adnexal mass is possible in the majority of women, but the probability of success is not readily predictable. In cases where the intended procedure has to be abandoned, the appropriate technique (e.g. staging laparotomy for ovarian cancer) or a second procedure (e.g. laparoscopy or laparotomy after bowel preparation) under general anaesthesia should be scheduled as soon as possible. Women who require an alternative more appropriate intervention or a second procedure are not excluded or withdrawn from the NOTABLE trial. The investigators will sensitively explain to them that follow-up information is still very important,

despite the change in treatment, and unless they wish to withdraw completely from the trial, they will be followed up.

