4.2. Concomitant interventions and treatments

It is anticipated that most women presenting with a suspected benign adnexal mass will require no further intervention other than removal of the adnexa. However, in some circumstances additional treatments may be considered necessary by the responsible clinician at the time of adnexal removal or subsequently. Surgical interventions in the form of endometrial ablation or hysterectomy may subsequently be necessary and the need for such interventions will be recorded. However, if the need for additional surgery *at the time* of surgery is indicated, then such patients are excluded for recruitment to the NOTABLE trial. All therapeutic interventions additional to removal of one or both adnexa will be recorded and as the trial is randomised we anticipate that these further interventions will be symmetrically applicable.

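### Section 3.1 takes the final eligibility decision during surgery, after allocation is known to an unblinded surgeon, which contradicts sections 3.2 and 3.5

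*Protocol*

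**What the plan says.** On when eligibility is settled, the protocol gives two answers.

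- **During surgery.** Section 3.1, describing what is explained to women before consent: "the final decision about eligibility will be taken during the surgical procedure and is dependent on the findings".
- **Before allocation.** Section 3.2: women "are eligible in the NOTABLE trial based on the findings of the ultrasound findings and will be randomised before the procedure". Section 3.5: "the randomised allocation will not be given until all eligibility and stratification data have been given".

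On who knows the arm at that moment:

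- Section 3.3 has the trial secretary obtain the allocation the day before surgery for a woman who is already eligible, and then: "The envelope will be opened by the nurse assistant on the day of surgery for practical logistic reasons".
- Section 4.1 has the principal investigator do every operation: "He is therefore not blinded".

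On what happens when surgery brings a surprise:

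- Section 4.1.3 considers "unexpected findings such as extensive adhesions or unexpected malignancy" and rules: "Women who require an alternative more appropriate intervention or a second procedure are not excluded or withdrawn from the NOTABLE trial".
- Section 4.3 follows up all consenting women whatever treatment they received, and 6.3 makes intention to treat the first analysis.
- Section 4.2, on additional surgery indicated at the time of the operation, says "then such patients are excluded for recruitment to the NOTABLE trial".

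**The concern.** Eligibility should be closed before anyone who judges it can know the arm. Section 3.1 puts the last judgement at a point where the surgeon knows the arm and, under 4.1.1 and 4.1.2, is inspecting the pelvis through the allocated route. What he finds may therefore depend on the technique, and what he decides may depend on the allocation.

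The document's own examples of unexpected findings, adhesions and malignancy, are also its examples of why a procedure may not be completed. If such women could be declared ineligible, the women removed would tend to be failures of the technique in use. Removing failures from the vNOTES arm makes the arms look more alike. In a superiority trial that would often work against the new treatment's claim; in a non-inferiority trial it works for it. With 66 women in all, a single case can matter.

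**Working it through.** **1. The order of events.**

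| Step | Section | Arm known to the surgeon? |
|---|---|---|
| Ultrasound review, consent, eligibility | 3.1, 3.2 | No |
| Allocation obtained, day before surgery | 3.3 | Not yet disclosed |
| Envelope opened, day of surgery | 3.3 | Yes, from here on |
| Access by the allocated route, inspection of the pelvis | 4.1.1, 4.1.2 | Yes |
| Final eligibility decision according to 3.1 | 3.1 | Yes |

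Sections 3.2 and 3.5 need eligibility to be complete before the third row; 3.1 places it in the last. Both cannot hold.

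**2. The plan's own figure.** Inputs from 6.1: success 0.95 in both arms, margin 0.15, power 80%, one-sided test. The alpha is not stated; one-sided 5% is inferred because it reproduces the result.

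n per arm = (1.645 + 0.842)² × 2 × 0.95 × 0.05 / 0.15² = 6.18 × 0.095 / 0.0225 = 26.1, rounded up to 27, so 54 in total. With 15% drop-out, 54 / 0.85 = 63.5, so 64. Both agree with 6.1. The final 66 is 33 per arm at 1:1.

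**3. What one exclusion could do.** This is hypothetical: the protocol plans no exclusions.

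- Decision rule (6.1, 6.3): non-inferiority if the upper limit U of the two-sided 95% interval for p_L − p_V (laparoscopy minus vNOTES) is below 0.15.
- Wald: U = p_L − p_V + 1.96 × √[p_L(1 − p_L)/n_L + p_V(1 − p_V)/n_V].
- Newcombe: U = p_L − p_V + √[(u_L − p_L)² + (p_V − l_V)²], where u_L is the upper Wilson limit for laparoscopy and l_V the lower Wilson limit for vNOTES.
- The protocol names no interval method, so both are shown.
- Truth: 0.95 for laparoscopy and 0.80 for vNOTES. The deficit equals the margin, so every conclusion of non-inferiority is an error.
- Error rate = sum over all (x_L, x_V) with U < 0.15 of Bin(x_L; 33, 0.95) × Bin(x_V; 33, 0.80).
- Exclusion: where an arm has at least one failure, one is removed, so x/33 becomes x/32.

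| Assumed exclusion | Wald | Newcombe |
|---|---|---|
| None | 4.2% | 2.2% |
| One vNOTES failure | 10.7% | 5.9% |
| One failure in each arm | 9.0% | 3.2% |

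**4. A single data set (illustrative counts).**

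- Wald, laparoscopy 32/33 and vNOTES 30/33: U = 0.0606 + 1.96 × 0.0583 = 17.5%, not shown.
- Wald, one vNOTES failure removed (30/32): U = 0.0322 + 1.96 × 0.0522 = 13.4%, shown.
- Newcombe, same counts: 20.8% and 17.3%, so the conclusion does not change.
- The Newcombe boundary lies one case further on: 31/33 gives 16.8% (not shown) and 31/32 gives 13.0% (shown).

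**The case against.** The strongest reply is that 3.1 only describes what women are told, as the reason for taking consent beforehand, and never says that a woman judged ineligible leaves the trial or the analysis. The operative rules point the other way: 4.1.3 keeps women whose procedure has to change, 4.3 follows everyone, and 6.3 analyses by intention to treat first. This stands. A reader might infer that the protocol plans to exclude women on operative findings with the arm known; the text does not support that.

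A reader might also take 4.2 as a second route to exclusion during surgery. Section 3.2 already lists a need for other uterine surgery among the exclusion criteria, and 4.2 can be read as restating it. Its wording is loose, not clearly contradictory.

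The one-arm exclusion in the table is a worst case. Adhesions and malignancy can turn up in either arm, and 4.1.3 speaks of both techniques. With one failure dropped from each arm the increase is smaller, and under Newcombe only about one percentage point (2.2% to 3.2%).

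What the reply does not remove is the direct conflict between 3.1 and both 3.2 and 3.5. Nor does the intention-to-treat label settle it, because a woman declared ineligible can be argued never to have entered the trial.

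**Conclusion.** The point holds as an internal contradiction about when eligibility is final. As written, 3.1 leaves room for exclusion after allocation by someone who knows the arm, although the later sections lean towards retention. It should be corrected.

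The size is conditional. If one failure were dropped, the false non-inferiority rate at the margin would rise from 4.2% to between 9.0% and 10.7% (Wald), or from 2.2% to between 3.2% and 5.9% (Newcombe); the lower end is one failure from each arm, the higher end one from vNOTES only. This assumes 33 analysed per arm and true success of 95% and 80%. How often exclusion would happen, if at all, cannot be known from the document. The single data sets show how sensitive a 66-woman trial is to one case; they are not error rates.

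A reader might go on to infer that the primary endpoint is undefined for a woman converted from the allocated technique whose mass comes out intact. The document does not support that as a fault: 5.2 read literally (mass removed, no rupture, no aspiration) gives a usable rule that fits intention to treat. The two vNOTES series described in 1.4 report no conversions (0/20 and 0/7).

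**What to change.** 1. In 3.1, delete the sentence or reword it so that trial eligibility is final before the envelope is opened, in line with 3.2 and 3.5. If the intention was to tell women that the operation itself may change with the findings, say that instead; it is a different matter from eligibility.
2. In 6.3, state that every randomised woman stays in the primary intention-to-treat analysis in her allocated arm, whatever the operative findings.
3. In 4.2, clarify that the exclusion refers to a need for additional surgery known before randomisation.

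These are wording changes. They alter neither the sample size nor the power, and they do not touch the surgeon's freedom to change the operation under 4.1.3.

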3.2. Determining eligibility

All women regardless of age and parity presenting with a symptomatic or asymptomatic persistent benign adnexal mass on clinical examination who provide consent to participation are eligible in the NOTABLE trial based on the findings of the ultrasound findings and will be randomised before the procedure.

The following inclusion/exclusion criteria will be applied to assess eligibility:

Inclusion criteria:

- All women regardless of age and parity with a symptomatic adnexal mass presumed to be benign based on ultrasound examination by applying the IOTA simple rules
- All women regardless of age and parity with an asymptomatic persistent adnexal mass presumed to be benign based on ultrasound examination by applying the IOTA simple rules

- Written informed consent obtained prior to surgery

Exclusion criteria:

- History of hysterectomy by any technique
- History of rectal surgery
- Suspected rectovaginal endometriosis
- Suspected endometriotic cyst
- Solid adnexal mass
- High suspicion of adnexal malignancy based on clinical, ultrasound or biochemical findings
- History of pelvic inflammatory disease, especially prior tubo-ovarian or pouch of Douglas abscess
- Active lower genital tract infection e.g. Chlamydia, N. gonorrhoeae
- Virginity
- Pregnancy
- Need for other uterine surgical intervention (i.e. endometrial ablation, resection, myomectomy or hysterectomy)
- Additional pathology necessitating hysterectomy
- Failure to provide written informed consent prior to surgery

Obesity (Body Mass Index or BMI > 30), nulliparity or large diameter of the cyst are not considered to be an exclusion criterion per se. We will only stratify for the diameter of the cyst because this parameter was perceived by the gynaecological surgeon as the most important one to influence the difficulty of the procedure. Stratification for three parameters in a small pilot randomised trial with a limited number of participants is not sensible.

3.3. Randomisation

If the woman is eligible for the NOTABLE trial, the trial secretary will obtain a randomised allocation the day before surgery. This will be done using a randomisation list generated by a free computer software program offered by Research Randomizer (<https://www.randomizer.org>). The random sequence generation will be concealed using sequentially numbered opaque sealed envelopes. The envelope will be opened by the nurse assistant on the day of surgery for practical logistic reasons. We will use stratified randomisation according to the cyst diameter. See 3.5 Stratification of randomisation.

3.4. Patients with strong preference for treatment

A minority of women will express a clear preference for one of both treatments (e.g. strong desire to have no scar) and for this reason will not wish to be randomised between surgical treatments. To investigate how outcomes vary by choice, these women could be followed up in exactly the same way as for those women randomised into the NOTABLE trial. We will however not do any formal non-randomised follow-up of these women for simple logistical reasons.

3.5. Stratification of randomisation

A blocked randomisation procedure will be used to avoid chance imbalances for the parameter 'cyst diameter'. We preferred not to use minimisation because this trial was not funded and we therefore could not afford to buy licenses for a computer-based algorithm for minimisation. Although parity and BMI may be prognostic parameters influencing the chances of the successful removal of the adnexal mass, we preferred to limit the stratification to one parameter for reasons of simplicity based on what is affordable to conduct the present research. It was not considered appropriate to use three strata in a small pilot study including a small number of participants.

To avoid any possibility of foreknowledge, the randomised allocation will not be given until all eligibility and stratification data have been given.

